8.4 Analyses

Analysis methodologies presented in this section will apply to all cohorts except otherwise specified. Each cohort will be analyzed separately and interdependently but pooling of certain cohorts may be performed.

8.4.1 Demographics and Baseline Characteristics

Demographic and baseline laboratory results will be summarized for all treated subjects by cohort (MSI-H, non-MSI-H, C3, C4, C5, and C6) and treatment (monotherapy and combination therapy, if applicable) using descriptive statistics.

8.4.2 Efficacy Analyses

8.4.2.1 Primary Endpoint Methods

The investigator-assessed ORR will be summarized by cohort and by treatment (monotherapy and combination therapy, if applicable). A response rate estimate and corresponding two-sided exact CI will be provided. For the reporting following a 2-stage design, the method proposed by Atkinson and Brown will be used to estimate a 90% CI. This confidence interval takes into account the group sequential nature of the two-stage Simon design, where applicable. Otherwise, the method of Clopper-Pearson will be used to estimate a 95% CI, regardless of the study design, if more subjects were treated beyond the sample size per the original Simon's 2-stage design.

Within each cohort, ORR will be further characterized by the DOR and rate of CR. DOR will be summarized for subjects who achieve confirmed PR or CR using the Kaplan-Meier (KM) product-limit method. Median values of DOR, along with two-sided 95% CI (based on the log-log transformation), will also be calculated. Investigator-assessed CR will be summarized by cohort and by treatment (monotherapy and combination therapy, if applicable). An estimate of complete response rate (CRR) and corresponding two-sided 95% exact CI will be provided using Clopper-Pearson method.

8.4.2.2 Secondary Endpoint Methods

ORR based on IRRC assessment will be summarized similarly as above and will be characterized by IRRC-assessed DOR and IRRC-assessed CRR similarly as above.

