Table 4: Two-sided 95% exact CI using Clopper-Pearson method based on the number of observed responses out of 40 subjects (For C6 Cohort)

The number of observed responses	6	7	8	9	12
Observed Response Rate	6/40 (15.0%)	7/40 (17.5%)	8/40 (20.0%)	9/40 (22.5%)	12/40 (30.0%)
95% exact CI	(5.7%, 29.8%)	(7.3%, 32.8%)	(9.1%, 35.6%)	(10.8%, 38.5%)	(16.6%, 46.5%)

Endpoints:

The primary endpoint is investigator-assessed ORR in each cohort. It is defined as the number of subjects with a best overall response (BOR) of confirmed CR or PR, according to RECIST 1.1 criteria, divided by the number of treated subjects in the related cohort. The secondary endpoint is IRRC-assessed ORR in each cohort. It is defined as the

Protocol Amendment No: 09

Date: 27-Aug-2021 25

number of subjects with a best overall response (BOR) of confirmed CR or PR, according to RECIST 1.1 criteria, divided by the number of treated subjects in the related cohort.

Analyses:

In each cohort, the investigator-assessed ORR will be further characterized by the investigator assessed duration of response (DOR) and rate of complete response (CR). A response rate estimate and corresponding two-sided 95% exact CI will be provided. The method proposed by Atkinson and Brown will be used to estimate the CI. This confidence interval takes into account the group sequential nature of the two-stage Simon design, where applicable. The method of Clopper-Pearson will be used otherwise if more subjects were treated beyond the sample size per the original Simon's 2-stage design. Within each cohort, ORR will be further characterized by the duration of response (DOR) and rate of complete response (CR). DOR will be summarized for subjects who achieve confirmed PR or CR using the Kaplan-Meier (KM) product-limit method. Median values of DOR, along with two-sided 95% CI (based on the log-log transformation), will also be calculated. Investigator-assessed CR will be summarized by cohort and by treatment (monotherapy and combination therapy, if applicable). An estimate of complete response rate (CRR) and corresponding two-sided 95% exact CI will be provided using Clopper-Pearson method.

ORR based on IRRC assessment will be summarized similarly as above and will be characterized by IRRC-assessed DOR and IRRC-assessed CRR similarly as above.

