All subjects will undergo screening evaluations to determine eligibility within 28 days prior to the start of therapy. A baseline tumor imaging assessment will be performed prior to the start of therapy. Tumor tissue must be provided for biomarker analysis. Central lab must provide IVRS with confirmation of receipt of evaluable tumor tissue prior to study treatment. Subjects whose repeat testing does not confirm MSI-H status will be replaced but will be allowed to continue on study therapy. Subjects on C3 will be accepted with a valid local MSI result.

Treatment beyond initial investigator-assessed progression is permitted if the subject has an investigator-assessed clinical benefit and is tolerating study drug, see Section 4.3.8. The investigator-assessed tumor response based on RECIST 1.1 criteria will be used to guide the stage 1 decision and for the primary analysis of the ORR. In addition, an independent radiology review

Protocol Amendment No: 09

Approved v1000 930073805 10.0

committee (IRRC) will perform central review of the imaging per RECIST 1.1 criteria upon study completion. Details will be included in the IRRC charter.

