If accrual to the combination arm is opened to the MSI-H cohort as specified above, stage I of the Simon two-stage design will be initiated in the combination arm with 19 treated subjects (cStage 1). If there are 6 or fewer responses in these first 19 treated subjects, accrual to the combination arm will be stopped. Otherwise, approximately 29 additional subjects will be accrued to the combination arm (cStage 2) to target a total of 48 subjects treated with combination therapy.

Subjects whose repeat testing does not confirm MSI-H status will be replaced in order to obtain the required number of subjects in each stage of the Simon design. Note that because of the delay in obtaining the centrally evaluated MSI status, more than 48 subjects may be treated with monotherapy and combination therapy in these initial cohorts.

The null hypothesis will be rejected if 20 or more responses are observed in 48 treated subjects in the open arm (nivolumab monotherapy and/or nivolumab/ipilimumab combination). Within a

given treatment arm, this design yields a one-sided type I error rate of 5% and power of 90% when the true response rate is 52%.

Sample size determination for Cohort C3:

The sample size determination for Cohort C3 was not based on power consideration but to provide precision on estimation of ORR. Saltz and coworkers reported ORR of 49% and 38% in chemotherapy group, per investigator assessment and per independent response review committee assessment, respectively, in this patient population. Table 8.1-1 presents the 95% CI for ORR ranging from 45% to 65%, which are considered meaningful clinical outcome, with a sample size of 30 subjects.

Table 8.1-1: Interval Estimation and Coverage Probability -Clopper-Pearson Method (95% Confidence Interval)

Sample size	Number of responses	Response rate	Confidence interval
30	13	0.43333	(0.2546, 0.6257)
30	14	0.46667	(0.2834, 0.6567)
30	15	0.50000	(0.3130, 0.6870)
30	16	0.53333	(0.3433, 0.7166)
30	17	0.56667	(0.3743, 0.7454)
30	18	0.60000	(0.4060, 0.7734)
30	19	0.63333	(0.4386, 0.8007)
30	20	0.66667	(0.4719, 0.8271)

Sample size determination for Cohort C5:

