8.5 Interim Analyses

For each treatment arm in the MSI-H cohort (mStage 1 monotherapy and combination therapy, if applicable), one interim analysis of investigator-assessed ORR will be performed on the first 19 treated subjects with confirmed MSI-H CRC. If there are 6 or fewer responses in these first 19 treated subjects, accrual to the corresponding treatment arm will be stopped. Otherwise, approximately 29 additional confirmed MSI-H subjects will be accrued into the corresponding treatment arm to target a total of 48 treated subjects in that arm.

Subjects in mStage 1 or cStage 1 who remain on treatment should complete a 24-week follow up for an assessment of ORR. The final analyses of these initial MSI-H cohort will take place after sufficient follow-up has been achieved for most or all of the subjects (eg, 6 months of treatment for the monotherapy cohort and 9 months of treatment for the combination therapy cohort).

Anticipating a different enrollment rate in cohorts C3-C6, these cohorts will be analyzed independently. Interim analyses will be conducted approximately 6 months after the last subject treated in the corresponding cohort.

In addition, other interim analyses may be conducted to seek initial efficacy signal or for external data disclosure for these cohorts.

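### IRRC-assessed ORR inherits a two-stage interval built for the investigator-gated count; in an MSI-H arm analysed at exactly 48 subjects the limits do not fit the IRRC data

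*Combined protocol and SAP*

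**What the plan says.** Section 8.4.2.1 sets the interval for investigator-assessed ORR: "For the reporting following a 2-stage design, the method proposed by Atkinson and Brown will be used to estimate a 90% CI". It justifies this by the sequential nature of the Simon design and adds a second branch: "Otherwise, the method of Clopper-Pearson will be used to estimate a 95% CI, regardless of the study design, if more subjects were treated beyond" the original Simon sample size. Section 8.4.2.2 then covers the IRRC endpoint in one line: "ORR based on IRRC assessment will be summarized similarly as above". The Synopsis (Analyses) uses the same back-reference but a different confidence level: "two-sided 95% exact CI will be provided. The method proposed by Atkinson and Brown will be used to estimate the CI". Neither place gives an IRRC-specific interval.

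On who decides continuation, Section 3.1 says: "The investigator-assessed tumor response based on RECIST 1.1 criteria will be used to guide the stage 1 decision". Section 8.5 agrees: "one interim analysis of investigator-assessed ORR will be performed on the first 19 treated subjects with confirmed MSI-H CRC". Section 3.1 also places the IRRC's central review at study completion. Section 8.1 foresees over-accrual while central MSI results are awaited: "more than 48 subjects may be treated with monotherapy and combination therapy in these initial cohorts".

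**The concern.** A two-stage exact interval is computed on a restricted sample space. Either the arm stops with 0 to 6 responders of 19, or it continues with at least 7 and yields a total out of 48. That restriction describes the investigator count, because the investigator count made the decision. It does not describe the IRRC count. An arm can pass on 7 or more investigator responders while the IRRC later confirms 6 or fewer of those 19.

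The IRRC ORR is the independent check on an open-label, investigator-read primary endpoint. That check matters most when the IRRC reads lower, and low IRRC counts are where the mismatch moves both limits upward. What is at stake is the honesty of the reported error bars on a secondary endpoint, not a decision rule.

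**Working it through.** **Inputs.** Section 8.1: n1 = 19, continue if at least 7 respond, n = 48 (so n2 = 29), reject if at least 20 respond, null ORR 30%, alternative 52%. Section 8.4.2.1: 90% level. Synopsis: 95% level.

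**Reproducing the plan's figures.** P(X1 ≥ 7 and X1 + X2 ≥ 20) is 0.0485 at p = 0.30 and 0.9036 at p = 0.52, which agrees with the stated 5% and 90%.

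**Two-stage limits.** Assumption: outcomes are ordered with the stopped results first (0 to 6 of 19), then by total out of 48. The documents do not state the ordering. For a total S, with tail area a (0.05 for a 90% interval, 0.025 for 95%):

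- the lower limit solves P(X1 ≥ 7, X1 + X2 ≥ S) = a;
- the upper limit solves P(X1 ≤ 6) + P(X1 ≥ 7, X1 + X2 ≤ S) = a.

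As a check, the 90% lower limit at 20/48 is 30.1%, consistent with the rejection rule.

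**The floor.** The upper-limit equation always contains P(X1 ≤ 6). That term alone equals 0.05 at p = 0.530 and 0.025 at p = 0.566. In an arm that reaches 48, the upper limit therefore cannot go below 53.0% (90% level) or 56.6% (95% level).

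**Limits at the 90% level.**

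| IRRC count | Estimate | Two-stage | Clopper-Pearson |
|---|---|---|---|
| 8/48 | 16.7% | 18.8-53.0% | 8.6-28.1% |
| 12/48 | 25.0% | 19.8-53.0% | 15.1-37.3% |
| 16/48 | 33.3% | 23.9-53.2% | 22.2-46.1% |
| 18/48 | 37.5% | 26.8-54.1% | 25.8-50.4% |
| 20/48 | 41.7% | 30.1-56.1% | 29.6-54.5% |
| 24/48 | 50.0% | 37.5-62.8% | 37.4-62.6% |

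At 8/48 the interval excludes its own point estimate. At the 95% level it does not (lower limit 16.3%), but at 7/48 it does (estimate 14.6%, lower limit 16.3%). An IRRC total below 7 has no place in the method's sample space.

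**Coverage of the nominal 90% interval, given that the arm continues.** This was simulated. The true rates and the overlap between the two readings are assumptions. Independent means that IRRC response is unrelated to investigator response; nested means that every IRRC responder is also an investigator responder.

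| Investigator / IRRC ORR | Two-stage | Clopper-Pearson |
|---|---|---|
| 30% / 20% | 71% nested, 85% independent | 90%, 93% |
| 40% / 30% | 92%, 94% | 95%, 94% |
| 49% / 38% | 96%, 97% | 94%, 93% |
| 52% / 45% | 95-96%, 96% | 93%, 92% |

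In the first row, counts below 7 are given the limits for 7. If they are scored as misses instead, two-stage coverage is 68% nested and 72% independent. At 49%/38% with 36% responding on both readings, 31% of continuing arms have an IRRC Stage 1 count of 6 or fewer, and mean width is 27.6 points against 24.4.

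**The case against.** Several points on the other side stand.

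- **The Clopper-Pearson branch.** A reader might infer that IRRC ORR always receives the two-stage interval. Section 8.4.2.1 switches to Clopper-Pearson at 95% once more than the Simon number are treated, and the back-reference carries that switch to the IRRC as well. Over-accrual is foreseen: unconfirmed subjects are replaced but may stay on therapy. When the switch operates, the problem does not arise.
- **The floor is conditional.** That the upper limit can never fall below 53% is also too strong. An arm stopped at Stage 1 can be lower (5/19 gives 47.6%). Ordering outcomes by observed proportion would give 42.0% at 12/48.
- **A lower IRRC rate does not by itself distort the interval.** Size depends on the IRRC count, not on the sign of the gap. At 25/48, near the design alternative, the limits are 39.4-64.7% against 39.4-64.6%.
- **At 49%/38% the interval is conservative.** The lower limit exceeds the true rate in about 3.6% of continuing arms under both methods (36% overlap). The only cost there is a wider upper side. The 49%/38% pair is itself a first-line chemotherapy benchmark cited for the single-stage Cohort C3, so it is only an illustration here.
- **The investigator gate does act partly on IRRC data.** In that scenario it lowers the chance of an IRRC Stage 1 count of 6 or fewer from 37% to 31%. Clopper-Pearson ignores this selection.
- **No test is involved.** A reader might see 30.1% against 29.6% at 20/48 as a false rejection of the null. The documents attach no hypothesis test to IRRC ORR, and at 95% neither lower limit exceeds 30% (28.1% and 27.6%).

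None of this supplies a reason to use the two-stage interval for the IRRC count at the planned size of 48. It limits when the error arises and how large it is.

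**Conclusion.** Wrong as written, of moderate to minor severity. For an MSI-H arm that continues and is analysed at exactly 48, the plan assigns the IRRC ORR an interval whose sample space was set by a different assessor's count. The distortion is material below roughly 20/48 and negligible from 24/48. It shows as over-wide upper limits at moderate IRRC rates and as under-coverage at low ones.

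The numerical limits rest on ordering outcomes by stage and response count. The coverage figures rest on assumed true rates and assumed overlap between the two readings. Whether an arm is analysed at exactly 48 cannot be told from the documents. The type I error and power of the investigator-based design are unaffected.

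**What to change.** In Section 8.4.2.2 and in the Synopsis, replace the back-reference for the interval with:

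*IRRC-assessed ORR uses the Clopper-Pearson exact interval in all cohorts, whichever interval is used for investigator-assessed ORR. The Atkinson-Brown interval is used only for investigator-assessed ORR, on which the Stage 1 decision is based.*

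State the confidence level in that sentence, and reconcile the 90% in Section 8.4.2.1 with the 95% in the Synopsis for the two-stage interval itself.

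The cost is one sentence and a line of programming, using a method the plan already contains. The IRRC lower limit becomes slightly less favourable (29.6% instead of 30.1% at 20/48, 90% level). Clopper-Pearson does not model the partial selection by the investigator gate, but its simulated coverage stays at about 90-95% in every scenario examined.

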8.4.2.3 Exploratory Endpoint Methods

PFS and OS will be summarized descriptively for each cohort using the KM product-limit method. Median values of PFS and OS, along with two-sided 95% CI (based on the log-log transformation), will also be calculated.

8.4.3 Safety Analyses

Safety analyses will be performed in all treated subjects by cohort (MSI-H, non-MSI-H independent safety cohort, and C3, C4, C5, and C6) and treatment (monotherapy and combination therapy, if applicable). Descriptive statistics of safety will be presented using NCI CTCAE version 4.0. All on-study AEs, drug-related AEs, SAEs, and drug-related SAEs will be tabulated using worst grade per NCI CTCAE v4.0 criteria by system organ class and MedDRA preferred term. On-study lab parameters including hematology, chemistry, liver function, thyroid function, and renal function will be summarized using worst grade per NCI CTCAE v4.0 criteria.

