- 5. Subjects with a condition requiring systemic treatment with either corticosteroids (> 10 mg daily prednisone equivalents) or other immunosuppressive medications within 14 days of study drug administration. Inhaled or topical steroids and adrenal replacement doses > 10 mg daily prednisone equivalents are permitted in the absence of active autoimmune disease.

Re-initiation of Treatment for MSI-H Cohorts

Subjects in MSI-H cohorts who discontinue study treatment at Maximal Clinical Benefit, (Section 3.1.4.1) are permitted to re-initiate treatment, if disease progression defined by RECIST criteria occurs within 1 year (≤52 weeks) and protocol-defined criteria (Section 4.3.9) are met.

Study Assessments: The primary endpoint of this study is ORR which is based on tumor assessments at baseline and then at 6 weeks from first dose which continue every 6 weeks for the first 24 weeks and every 12 weeks thereafter until disease progression (investigator-assessed RECIST 1.1-defined progression) or treatment discontinuation, whichever occurs later.

Statistical Considerations:

Sample Size: This study will consist of 5 cohorts: non-MSI-H safety cohort, MSI-H cohort (Cohort N and Cohort N+I), Cohort C3 (MSI-H subjects who have not had prior therapy for their metastatic disease), MSI-H Cohort C5 Cohort and non-MSI-H Cohort C6. It is expected to treat up to approximately 96 central-pathology-lab-confirmed subjects (up to 29 non-MSI-H and up to 67 MSI-H) for the initial non-MSI-H and MSI-H cohorts. It is expected to treat approximately 30 subjects in cohort C3. It is expected to treat approximately 40 MSI-H subjects in C5 Cohort and 40 non-MSI-H subjects C6 Cohort.

Sample size determination for non-MSI-H and MSI-H cohorts:

The MSI-H cohort will include subjects who are defined as MSI-H based on standard diagnostic testing documented in the subject's medical history and prospectively confirmed in the current study by repeat testing using a polymerase chain reaction (PCR) test.

The non-MSI-H safety cohort will include all subjects testing non-MSI-H by the repeat PCR test, including those who were MSI-H by medical history but not confirmed by repeat testing.

For the non-MSI-H safety cohort, sample size is not based on power considerations and will depend on the observed toxicity.

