Safety analyses will be performed in all treated subjects by cohort (MSI-H, non-MSI-H, and C3) and treatment (monotherapy and combination therapy, if applicable). Descriptive statistics of safety will be presented using NCI CTCAE version 4.0. On-study AEs will be tabulated using worst grade per NCI CTCAE v4.0 criteria by system organ class and MedDRA preferred term. On-study lab parameters including hematology, chemistry, liver function, thyroid function, and renal function will be summarized using worst grade per NCI CTCAE v4.0 criteria.

REFERENCES

¹ Saltz LB, Clarke S, Díaz-Rubio E, et al: Bevacizumab in combination with oxaliplatin-based chemotherapy as first-line therapy in metastatic colorectal cancer: a randomized phase III study. J Clin Oncol. 2008;26:2013-2019.

TABLE OF CONTENTS

TITLE PAGE
DOCUMENT HISTORY
OVERALL RATIONALE FOR PROTOCOL AMENDMENT 09:
SUMMARY OF KEY CHANGES FOR PROTOCOL AMENDMENT 09
SYNOPSIS
TABLE OF CONTENTS

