1.3.3 Exploratory Objectives

- To determine the safety and tolerability [defined as toxicity rates (worst CTC grade per subject) of adverse events and specific laboratory tests] of nivolumab monotherapy (mStage 1 and 2), nivolumab in combination with ipilimumab (cStage 1 and 2, and C3 Cohort) in subjects with metastatic CRC, nivolumab in combination with anti-LAG-3 antibody (BMS-986016) in subjects with metastatic dMMR/MSI-H mCRC, or nivolumab in combination with daratumumab in subjects with metastatic non-MSI-H (pMMR) mCRC.
- To estimate PFS and OS for subjects with metastatic CRC who have received nivolumab monotherapy (mStage 1 and 2), nivolumab in combination with ipilimumab (cStage 1 and 2, and C3 Cohort, nivolumab in combination with anti-LAG-3 antibody (BMS-986016) in subjects with metastatic dMMR/MSI-H mCRC or nivolumab in combination with daratumumab in subjects with metastatic non-MSI-H (pMMR) mCRC.
- To evaluate the safety and tolerability of nivolumab in combination with ipilimumab in subjects with metastatic non-MSI-H CRC in the safety cohort.
- To evaluate investigator-assessed and IRRC-assessed ORR of nivolumab in combination with ipilimumab in subjects with metastatic non-MSI-H CRC in the safety cohort.
- To characterize the PK of nivolumab monotherapy, PK of nivolumab, ipilimumab, BMS-986016, and daratumumab when combined, and to explore exposure-response relationships.

• To characterize the immunogenicity of nivolumab monotherapy, immunogenicity of nivolumab, ipilimumab, BMS-986016, and daratumumab when combined.

- To evaluate the pharmacodynamic activity of nivolumab monotherapy, nivolumab in combination with ipilimumab, nivolumab in combination with anti-LAG-3 antibody (BMS-986016), and nivolumab in combination with daratumumab in subjects with metastatic CRC in the peripheral blood and tumor tissue as measured by flow cytometry, immunohistochemistry, soluble factor analysis, and gene expression (microarray technology, quantitative RT-PCR).
- To investigate the association between biomarkers in the peripheral blood and tumor tissue, such as PD-L1 expression, with safety and efficacy for subjects with advanced or metastatic tumors treated with nivolumab monotherapy, nivolumab in combination with ipilimumab, nivolumab in combination with anti-LAG-3 antibody (BMS-986016), and nivolumab in combination with daratumumab.
- To characterize the discordance rate between repeat MSI testing and prior MSI testing in subjects.

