3.1.2 Non-MSI-H Subjects (Independent Safety Sub-Trial)

An independent safety sub-trial in non-MSI H subjects will inform the safe and tolerable dose level for cStage 1 in subjects with MSI-H mCRC. The combination of nivolumab and ipilimumab is already being evaluated in Phase 3 in advanced melanoma and has more recently been tested in NSCLC and RCC. This regimen is expected to also be tolerable in mCRC, but given the potential for gastrointestinal toxicities with ipilimumab and nivolumab (eg, colitis), a dose escalating safety phase will assess the safety and tolerability of nivolumab in combination with ipilimumab and evaluate different doses of each agent. Enrollment in the non-MSI-H N+I Safety Sub Trial will occur in parallel to mStage 1.

3.1.2.1 Dose Escalating Safety Evaluation for Nivolumab in Combination with Ipilimumab in non-MSI- H Subjects

Table 3.1.2.1-1 contains the dose levels for the non-MSI-H dose escalation safety cohort.

Table 3.1.2.1-1: Dose Cohort for Safety non-MSI-H N+I			
Dose Cohort Level	Nivolumab (mg/kg)	Ipilimumab (mg/kg)	
-1	0.3	1	
1	1	1	
2a	1	3	
2b	3	1	

The first dose cohort will be Dose Level 1, 1 mg/kg each of nivolumab and ipilimumab. If this combination is deemed tolerable, then subjects will be randomized (1:1) to one of two dose levels:

- Dose Level 2a (N1+I3): 1 mg/kg nivolumab + 3 mg/kg ipilimumab, or
- Dose Level 2b (N3 + I1): 3 mg/kg nivolumab + 1 mg/kg ipilimumab

The tolerable dose of the combination will be brought into an analogous 2-stage design if nivolumab monotherapy (mStage 1) does not have 7 or more responders out of the first 19 subjects.

If Level 1 is not tolerable, then Level -1 will be initiated. There will be no dose escalation beyond Levels 2a and 2b. Once the decision on the dose level for further investigation has been confirmed, that dosing level will be used in cStage 1 in subjects with MSI-H (Section 3.1.4.3).

Subjects need to be followed up for at least 6 weeks after start of study treatment before determination of the tolerability of a dose level. However, tolerability beyond 6 weeks may also be taken into consideration.

The criteria for tolerability for Dose Level 1 (and -1 if necessary) (Table 3.1.2.1-2) are based on drug-related adverse events leading to permanent discontinuation (listed in Section 4.3.6) and include:

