Dose Escalation Phase Dose Level 1	1 mg/kg Nivolumab 1 mg/kg Ipilimumab				

Protocol Amendment No: 09

Date: 27-Aug-2021

Table 3.1.2.1-3: Dosing Schedule for Arm nMSI-H N+I (Week 1-12) - Nivolumab + Ipilimumab Combination					
	Every 3 Week Dosing				
Study Part	Day 1 Dose 1/Week 1	Day 1 Dose 2/Week 4	Day 1 Dose 3/Week 7	Day 1 Dose 4/Week 10	
Dose Escalation Phase Dose Level 2a	1 mg/kg Nivolumab 3 mg/kg Ipilimumab				
Dose Escalation Phase Dose Level 2b	3 mg/kg Nivolumab 1 mg/kg Ipilimumab				

Table 3.1.2.1-4 contains the dosing schedule for Arm N+I weeks 13 and following.

Table 3.1.2.1-4: Dosing Schedule for Arm nMSI-H N+I (Week 13 and following) Nivolumab + Ipilimumab Combination Escalation Cohort				
Every 2 Week Dosing				
Day 1 Week 13		Day 1 Week 15	Day 1, Week 17, 19, 21 and every other week thereafter	
3 mg/kg Nivolum	nab	3 mg/kg Nivolumab	3 mg/kg Nivolumab	

Approximately 10 subjects with recurrent or metastatic nMSI-H CRC will be randomized (1:1) to Dose Level 2a (N1+I3) and Dose Level 2b (N3+ I1). Tolerability and safety of a treatment arm will be determined after all subjects per arm have completed four doses of the combination or have discontinued dosing prior to completing four doses. However, tolerability beyond four doses of the combination during the nivolumab monotherapy time period may also be taken into consideration. All subjects will continue to be followed for safety, progression, and overall survival after discontinuation of study medication. The tolerability criteria used to advance the dose level to the MSI-H cStage 1 will based on drug-related adverse events leading to permanent discontinuation (listed in Section 4.3.6) and include the following:

- If no more than one-third of the subjects in either Dose Level 2a or 2b permanently discontinue study medication prior to completing four doses due to treatment-related adverse events then this dose cohort will be deemed as tolerable.
- If more than one-third of subjects in either Dose Level 2a or 2b permanently discontinue study medication prior to completing four doses due to treatment-related adverse events, then the safety and tolerability of that treatment arm will be reviewed prior to randomizing any additional subjects. A decision will be made by the sponsor whether to continue enrollment or advance either treatment arm into the MSI-H Cohort, ie, cStage 1.

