8 STATISTICAL CONSIDERATIONS

8.1 Sample Size Determination

This study will consist of 5 cohorts: non-MSI-H safety cohort, MSI-H cohort (Cohort N and Cohort N+I), Cohort C3 (MSI-H subjects who have not had prior therapy for their metastatic disease), Cohort MSI-H C5, and Cohort non-MSI-H C6. All information pertaining to the C4 cohort was added via a site-specific Amendment 06. It is expected to treat up to approximately 96 subjects (up to 29 non-MSI-H and up to 67 MSI-H) for the initial non-MSI-H and MSI-H cohorts. It is expected to treat approximately 30 subjects in cohort C3. It is expected to treat approximately 40 MSI-H subjects in C5 Cohort and 40 non-MSI-H subjects C6 Cohort.

Sample size determination for the non-MSI-H safety Cohort and MSI-H Cohort:

The MSI-H cohort will include subjects who are defined as MSI-H based on standard diagnostic testing documented in the subject's medical history and prospectively confirmed in the current study by repeat testing using a PCR test.

The non-MSI-H cohort will include all subjects testing non-MSI-H by the repeat PCR test, including those who were MSI-H by medical history but not confirmed by repeat testing.

For the non-MSI-H safety cohort, sample size is not based on power considerations and will depend on the observed toxicity.

For the MSI-H cohort, a Simon optimal two-stage design will be used to test the null hypothesis that the true ORR is $\leq 30\%$ (not considered clinically compelling) with either nivolumab monotherapy or the combination of nivolumab/ipilimumab. In the first stage (mStage 1), 19 subjects will be treated with nivolumab monotherapy. If there are 2 or fewer responses in these first 19 treated subjects, the protocol will be closed to further enrollment. If there are more than 2 but less than 7 responses in the first 19 treated subjects, accrual to the monotherapy arm will be stopped, and the combination arm will be opened for accrual. Otherwise, if there are 7 or more responses in the first 19 treated subjects, approximately 29 additional subjects will be accrued to the monotherapy arm (mStage 2) to target a total of 48 treated subjects.

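### Section 8.4.3 puts every dose level of the non-MSI-H safety cohort into one combination column, so no safety table it describes is by dose

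*Combined protocol and SAP*

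**What the plan says.** Section 8.4.3 gives the rule for the safety tables: "Safety analyses will be performed in all treated subjects by cohort (MSI-H, non-MSI-H independent safety cohort, and C3, C4, C5, and C6) and treatment". The parenthesis that follows defines treatment as monotherapy or combination therapy. The Synopsis has a shorter form of the same rule: "Safety analyses will be performed in all treated subjects by cohort (MSI-H, non-MSI-H, and C3) and treatment (monotherapy and combination therapy, if applicable". Neither names dose level.

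Sections 3.1.2.1 and 3.1.4.4 define the regimens of the non-MSI-H safety cohort. In mg/kg, nivolumab first, they are Level 1 at 1+1, Level 2a at 1+3, Level 2b at 3+1 and a conditional Level -1 at 0.3+1. If Level 1 is tolerable, subjects are randomised 1:1 between 2a and 2b.

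Section 3.1.2 says that this phase is there to "assess the safety and tolerability of nivolumab in combination with ipilimumab and evaluate different doses of each agent". For the randomised levels, Section 3.1.2.1 makes the arm the unit of judgement: "Tolerability and safety of a treatment arm will be determined after all subjects per arm have completed four doses of the combination". The cohort's own safety objective, in Section 1.3.3, does not mention dose: "To evaluate the safety and tolerability of nivolumab in combination with ipilimumab in subjects with metastatic non-MSI-H CRC in the safety cohort".

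**The concern.** The tables use a coarser unit than the sub-trial they report. The sub-trial was built to look at different doses of two drugs, and it randomises between two arms in which each drug's dose differs threefold. A table split only into monotherapy and combination cannot separate these arms, because both are combinations.

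At stake is what a reader of the report can learn about tolerability by dose. Rates at 1+1 and 1+3, and the descriptive side-by-side view of 2a and 2b, would be absent from the tables that the plan describes. A pooled rate would belong to no regimen that anyone received.

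**Working it through.** The plan states no figure on this point, so there is none to reproduce. The check has two parts: applying the grouping rule to the regimens, and working out what the resulting column contains.

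**Applying the rule**

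| Level (3.1.2.1, 3.1.4.4) | Nivolumab + ipilimumab, mg/kg | Column under 8.4.3 |
|---|---|---|
| -1 (only if Level 1 is not tolerable) | 0.3 + 1 | combination |
| 1 | 1 + 1 | combination |
| 2a (randomised) | 1 + 3 | combination |
| 2b (randomised) | 3 + 1 | combination |

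All levels fall in one cell. The treatment factor makes no distinction among the subjects of this sub-trial.

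**Does other text supply the split?**

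- Section 8.3.3 refers to event incidence by treatment arm. The phrase closes the sentence that lists mStage, cStage, C3, C5 and C6. The non-MSI-H nivolumab plus ipilimumab subjects come in the next sentence, without that wording.
- Sections 8.3.3, 8.4.5 and 8.4.7.2 leave particular details to the SAP. Section 8.4.3 does not, and the combined document contains no SAP section with a dose-level split.

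**Make-up of the column (escalation subjects only)**

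Inputs:

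- L1, the number at Level 1, is 3, 6 or 9 (Table 3.1.2.1-2).
- m, the number per randomised arm, is about 5 or about 10. Section 3.1.2.1 says that approximately 10 subjects are randomised 1:1, which can be read as a total or as a number per arm.
- Level -1 is left out because it is conditional.

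Formulas: N = L1 + 2m; share of 1+1 = L1/N; share of 1+3 = share of 3+1 = m/N.

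| L1 | m | N | 1+1 | 1+3 | 3+1 |
|---|---|---|---|---|---|
| 3 | 5 | 13 | 3/13 = 23.1% | 5/13 = 38.5% | 38.5% |
| 6 | 5 | 16 | 6/16 = 37.5% | 5/16 = 31.3% | 31.3% |
| 9 | 5 | 19 | 9/19 = 47.4% | 5/19 = 26.3% | 26.3% |
| 3 | 10 | 23 | 3/23 = 13.0% | 10/23 = 43.5% | 43.5% |
| 6 | 10 | 26 | 6/26 = 23.1% | 10/26 = 38.5% | 38.5% |
| 9 | 10 | 29 | 9/29 = 31.0% | 10/29 = 34.5% | 34.5% |

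The ranges are N = 13 to 29, 1+3 and 3+1 each 26% to 44%, and 1+1 13% to 47%. The last row matches the ceiling of 29 non-MSI-H subjects in Section 8.1 (9 + 10 + 10 = 29). That favours about 10 per arm but does not settle it, because 29 is a maximum.

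The pooled event rate is the average of the level-specific rates, weighted by these shares. No regimen makes up more than 47% of the column, so the pooled figure cannot stand in for any one of them.

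**The case against.** The strongest reply is that 8.4.3 is a short paragraph setting minimum groupings. Column layout normally sits in a SAP and its table shells, and a dose-level split may be there. That is possible, and nothing in 8.4.3 forbids a finer split. But 8.4.3 states a rule without deferring to another document, and the text available does not refine it.

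A second reply is that the protocol calls 2a and 2b arms, so the by-arm incidence in Section 8.3.3 could cover them. That is a plausible reading, though not the natural one given the sentence order, and 8.4.3 does not carry it through.

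Third, little follows in practice. This stands:

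- Under Section 3.1.2.1, tolerability is judged per level, and the sponsor reviews adverse events and efficacy to choose between 2a and 2b if both are tolerable.
- Section 1.4.2.2 describes the trial as non-comparative.
- Safety at 3+1 can be read in the MSI-H combination arm, since Table 4.3-2 gives 3+1 as the cStage dose.
- Separate columns would be small.

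A reader might also infer that the column is mixed with MSI-H subjects reclassified after testing. Section 8.1 counts in the non-MSI-H cohort subjects "including those who were MSI-H by medical history but not confirmed by repeat testing", and Section 3.1 adds "Subjects whose repeat testing does not confirm MSI-H status will be replaced but will be allowed to continue on study therapy". The documents do not establish this mixing:

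- Section 8.4.3 names the independent safety cohort, which can mean the sub-trial of Section 3.1.2 alone.
- Section 8.2 also defines the MSI-H cohort by local testing, so the placement of discordant subjects is unclear.
- No number of such subjects is given, and 9 + 10 + 10 escalation subjects already fill the stated ceiling of 29.

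**Conclusion.** The point holds as a gap in descriptive safety reporting. Under the stated grouping, three dose regimens, or those opened if the escalation went differently, share one combination column. That column is 26% to 44% each of 1+3 and 3+1 and 13% to 47% of 1+1, for N = 13 to 29. Rates at 1+1 and 1+3 appear in no table that 8.4.3 describes.

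The shares rest on the Level 1 sizes in Table 3.1.2.1-2, on either reading of the randomised numbers, on Level -1 staying closed, and on the column holding escalation subjects only. The conclusion also assumes that no SAP outside the reviewed text adds the split; confidence is medium for that reason.

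It would go too far to infer that the dose choice was compromised or that an objective fails. Dose selection runs on its own per-level rules, and the objective in Section 1.3.3 can be met with a pooled table. This is a cheap improvement and not a necessary correction.

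**What to change.** Add to Section 8.4.3 and to the safety paragraph of the Synopsis:

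> For the non-MSI-H independent safety cohort, safety tables will be presented descriptively by assigned dose level, for the levels opened, with Dose Levels 2a and 2b side by side as randomised. No test between arms will be made. Any pooled column is secondary.

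If a SAP already sets this out, a cross-reference in 8.4.3 is enough.

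The cost is wording and table shells. Level and arm are assigned under Section 3.1.2.1, so no new data are needed even though Section 3.1 describes the safety cohort as completed. The downside is imprecision in columns of about 3 to 10 subjects: the exact (Clopper-Pearson) 95% interval is 6.7% to 65.2% for 3/10 and 5.3% to 85.3% for 2/5. For that reason the tables should stay descriptive, and a pooled column can be kept as a supplement.
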